### **13.3 Statistical Methods**

Descriptive statistics (number of observations, mean, and standard deviation, minimum and maximum) will be calculated and presented for all quantitative responses. Frequency tables with number of observations, percentage of total and 95% confidence interval (score method) for the percentage (as applicable) will be created for discrete responses.

**Analysis for relative VAS pain:** a two-sided 95% confidence interval will be calculated for the average rating. A modeling approach may be used to adjust for the pair order effect, BD order effect within pair (due to the often-observed bias towards favoring the last pen needle used in a pair), abdomen site effect and random subject effect. Results will be tested for non-inferiority, followed by superiority:

---

If the lower bound of the CI is  $> -10\text{mm}$ , we can conclude in non-inferiority  
If the lower bound of the CI is  $> 0\text{mm}$ , we can conclude in superiority

Analysis for injection force via 5-point Likert scale: the responses will be converted to ratings of -2 – 2 (where positive ratings favor BD) and a two-sided 95% confidence interval will be calculated for the average rating. A modeling approach may be used to adjust for the pair order effect, BD order effect within pair, abdomen site effect and random subject effect. Results will be tested for superiority:

If the lower bound of the CI is  $> 0$ , we can conclude in superiority

Responses will also be converted to 3 categories: favoring Terumo Nanopass® (negative ratings), no difference (0 ratings) and favoring BD Nano™ PRO (positive ratings) and the difference in percentage of responses with a preference for BD vs Terumo needle calculated, adjusting for the “no preference” category.

Analysis for needle bending and leaking: analysis will be performed using a binary logistic regression with random subject effect and fixed pen needle effect, pair order effect, PN order effect within pair and abdomen site effect. The average difference in percentage of occurrence with BD PN and Terumo PN will be calculated with 95% confidence interval and assessed for statistical significance. The upper bound of the confidence interval will be compared to 0: superiority will be concluded given that the upper bound of the 95% confidence interval for the difference in proportions is  $< 0\%$ .

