2.3 Study Design

This is a subject partially blinded, block randomized, prospective, single-visit, multi-center study to compare user experiences with BD Nano™ PRO pen needle vs. the thinner commercially available Terumo Nanopass® pen needle. The study will include a minimum of 55 Japanese American study subjects having Type 1 or Type 2 diabetes. Study conduct will consist of one 60 to 120 minute Site visit in which pre-set doses of saline will be abdominally delivered by subjects via a reusable insulin pen device. All pen needles will be attached by Study Staff and pen needle outer cover and inner shield will be removed for subjects. Subjects are to perform 12 injections into the abdomen (6 pairs of injections). Pairs of injections will be evaluated and each pair will contain one BD Nano™ PRO and one Terumo Nanopass® pen needle. Subjects will not see pen needle labels or be informed which pen needle is being used to inject. The BD Nano™ PRO has a distinct configuration and subjects will most likely notice the difference vs the Terumo Nanopass®. Subjects will not be informed of the Terumo Nanopass® brand, length or gauge. The pen needle order within the pairs of injections will be randomized for each subject and the pairs will be randomized to various abdominal injection sites within each subject. Besides being informed of the requirement to insert the pen needles 'straight-in' (perpendicular), subjects will be instructed to use their usual injection technique.

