6.2.1 Analysis of Injection pain

A two-sided 95% confidence intervals will be calculated for the average rating. A modeling approach will be used to adjust for the pair order effect, BD order effect within pair (due to the often-observed bias towards favoring the last pen needle used in a pair), abdomen site effect and random subject effect. Results will be tested for non-inferiority, followed by superiority:

- If the lower bound of the CI is $> -10\text{mm}$, we can conclude in non-inferiority.
- If the lower bound of the CI is $> 0\text{mm}$, we can conclude in superiority.

```

> #####
> ## Example R code to fit a linear model
> #####
> ##
> ## fitting the model
> library(lme4)
> model.fit=lmer(vas_analysis ~ BD_NANO_ORDER + PAIR_ORDER + ABDOMEN_SITE
+                  +(1|SUBJ_ID),
+                  data=dataset, na.action=na.omit)
>

```

```

> ## Example for estimated pen needle subgroup means
> ##      if the lower CL is > -10, non-inferiority is satisfied
> ##      if the lower CL is > 0, superiority is satisfied
> library(emmeans)
> emmeans(model.fit, ~1)

```

```

1          emmean      SE      df lower.CL upper.CL
overall  24.10616 3.666296 145.14 16.85993 31.35238

```

Degrees-of-freedom method: kenward-roger
 Confidence level used: 0.95

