6.2.3 Needle Bending and Leakage

Analysis will be performed using a binary logistic regression with random subject effect and fixed pen needle type effect, pair order effect, PN order effect within pair and abdomen site effect. The average difference in percentage of occurrence with BD PN and Terumo PN will be calculated with 95% confidence interval and assessed for statistical significance. The upper bound of the confidence interval will be compared to 0: superiority will be concluded given that the upper bound of the 95% confidence interval for the difference in proportions is < 0%.

```

> #####
> ## Example R code to fit a logistic regression model
> #####
> ##
> ## fitting the model
> library(lme4)
> library(lsmeans)
> model.fit=glmer(leakage ~ PN +BD_NANO_ORDER+ PAIR_ORDER + ABDOMEN_SITE
+                   +(1|SUBJ_ID),
+                   data=dataset, na.action=na.omit, family="binomial",
+                   control = glmerControl(optimizer = "bobyqa"),nAGQ = 10)
> lsm.out<-lsmeans(model.fit, ~PN, type="response")
> confint(pairs(regrid(lsm.out)))

```

```

contrast           estimate      SE df asymp.LCL asymp.UCL
BD Nano - Terumo -0.00000001142909 2759378 NA  -5408282   5408282

```

Confidence level used: 0.95

6.2.4 Analysis of Exploratory Objectives (Delivery time, Total injection time, Needle Breaking, and Non-Comparative Questionnaire)

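### The leakage and bending code adjusts for whether BD Nano PRO came first or second in the pair, not for first versus second injection, so it does not deliver the within-pair order adjustment stated in the text; the effect on the needle comparison is small.

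*SAP*

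**What the plan says.** For bending and leakage, SAP 6.2.3 lists the fixed effects as "fixed pen needle type effect, pair order effect, PN order effect within pair and abdomen site effect", with a random subject effect. Protocol 13.3 has the same list: "fixed pen needle effect, pair order effect, PN order effect within pair and abdomen site effect". The example code in SAP 6.2.3 begins "model.fit=glmer(leakage ~ PN +BD_NANO_ORDER+ PAIR_ORDER + ABDOMEN_SITE" and then adds a random intercept for subject. It has no term for injection position and no interaction between needle and order.

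The same variable appears in the pain code in SAP 6.2.1, "model.fit=lmer(vas_analysis ~ BD_NANO_ORDER + PAIR_ORDER + ABDOMEN_SITE", where the text describes the adjustment as "BD order effect within pair (due to the often-observed bias towards favoring the last pen needle used in a pair".

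On design, SAP 2.3 states that "each pair will contain one BD Nano™ PRO and one Terumo Nanopass® pen needle" and that "The pen needle order within the pairs of injections will be randomized for each subject". SAP 2.4.2 has leakage and bending recorded after each injection, and force after each pair. For delivery time and total injection time, SAP 6.2.4.1 also promises an adjustment for needle order within the pair, but gives no code.

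**The concern.** The pain outcome is a single signed score per pair, and SAP 6.1.1 sets its sign by whether BD Nano PRO was injected second or first. A tendency to favour the last needle therefore pushes the score one way in BD-first pairs and the other way in BD-second pairs, and BD_NANO_ORDER picks this up.

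Leakage and bending are analysed injection by injection, which is why needle type (PN) is itself a predictor. Each pair contributes two rows. If BD_NANO_ORDER keeps its pain-model meaning, it is constant across those two rows while position changes from first to second. It then shifts both needles equally and cannot carry a position effect.

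Both endpoints carry superiority claims, decided by whether the upper 95% limit for the difference lies below zero, and leakage drives the sample size. Without the stated adjustment, the contrast relies on order being balanced among the injections that are analysed. The documents say that order is randomised but do not state exact balance. SAP 5.2 also removes individual injections with bleeding from the leakage analysis, which could disturb a balanced allocation.

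**Working it through.** **1. The plan's own figures.** SAP section 3 gives leakage of 20/298 = 6.7% (Terumo) and 3/297 = 1.0% (BD), a planned difference of 6.7 − 1.0 = 5.7 points. It states 90% power with 292 injections per needle. Drawing the two rates from Beta posteriors and applying a two-sided 5% test gives 89.3% (Beta(1,1) prior) or 90.7% (Beta(0.5,0.5) prior), so the figure reproduces on a Bayesian reading. The point below does not change it.

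**2. What the coded term can represent.** Code needle as p = +½ (BD) or −½ (Terumo), order as b = +½ (BD second) or −½ (BD first), and position as q = +½ (second injection) or −½ (first).

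| Pair | Row | p | b | q |
|---|---|---|---|---|
| BD first | BD | +½ | −½ | −½ |
| BD first | Terumo | −½ | −½ | +½ |
| BD second | Terumo | −½ | +½ | −½ |
| BD second | BD | +½ | +½ | +½ |

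In every row q = 2pb, so position is the needle-by-order interaction. Regressing q on p and b over one subject's 12 injections (three pairs in each order) gives R² = 0. Adding the product pb gives R² = 1.

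**3. What the coded term estimates.** Logistic data were simulated for 300 pairs, 600 runs per setting, with a base rate of 6.7% and no needle difference. Subject, site and pair-order effects were left out. At exact 50:50 order and an assumed position odds ratio of 3 (log odds ratio 1.10), the BD_NANO_ORDER coefficient averaged 0.02. A position covariate recovered 1.14.

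**4. Effect on the needle contrast when order is balanced.** In the same setting the average difference was +0.09 points under both codings, with standard errors of 2.14 points (as coded) and 2.12 points (position).

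**5. Effect at a 55:45 split.** If one needle is second in 55% of pairs, the unadjusted contrast carries (0.55 − 0.45) × (second-injection rate − first-injection rate). The position odds ratio of 2 is assumed.

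- Rates of 4.0% and 7.7% (odds 0.0417 and 0.0834, ratio 2.0): 0.10 × 3.7 = 0.37 points.
- Simulation with no needle difference: +0.33 points as coded and −0.10 with position, a gap of 0.43 points on the same data.
- Simulation near the planned difference: −5.64 points as coded and −5.90 with position, a gap of 0.26 points. Superiority was concluded in 97.2% and 97.7% of runs.

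The size is therefore about 0.3 to 0.4 points. These simulations put BD second more often and second injections leaking more, which counts against BD; with BD first more often, the sign reverses.

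**6. How likely such a split is.** If the order of 55 × 6 = 330 pairs were assigned independently, the SD of the BD-first proportion would be √(0.25/330) = 2.75 points. A split of 55:45 or worse in either direction is then 5/2.75 = 1.8 SD, with probability about 0.07.

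**The case against.** The best defence is that the SAP never defines BD_NANO_ORDER, the code is labelled an example, and the text is right: "pair order effect, PN order effect within pair and abdomen site effect" is worded differently from the BD order effect named for pain. If the leakage dataset recodes the variable as each injection's own position, nothing is wrong. This stands as a limit on certainty, but it does not remove the point. The variable's name and its use in the pain model both indicate a pair-level flag, and this code is the only specification of the term. The needed definition is missing on either reading.

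It is also fair that no position effect on leakage or bending is documented. The bias named in SAP 6.2.1 concerns subjects' ratings, whereas leakage is weighed and bending is scored by staff, with a new needle for each injection. With no position effect there is no bias. The plan nevertheless chose to specify the adjustment.

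Two stronger inferences are not supported. A reader might infer that the coding costs precision even when order is balanced. For leakage at exact balance, the estimates agree under both codings and the standard errors differ by about 1%, even at a position odds ratio of 3. A reader might also extrapolate to splits much wider than 55:45. The documents describe block randomisation, which may limit imbalance, and even under independent assignment of 330 pairs a split of 60:40 or worse has probability of only about 0.0003.

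**Conclusion.** The point holds as a mismatch between text and code. On the natural reading of BD_NANO_ORDER, the leakage and bending model does not adjust for first versus second injection, although the SAP and protocol both say that it does. The consequence is minor: essentially none under balanced order, and about 0.3 to 0.4 percentage points at 55:45 with an assumed position odds ratio of 2, against a planned 5.7 points. These sizes come from simple models without subject, site or pair-order effects. The primary pain analysis, the force analysis and the sample size are unaffected. It would go too far to infer that the superiority results for leakage or bending are biased: that needs both a position effect and an order imbalance, and the documents establish neither.

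**What to change.** In the leakage and bending model of SAP 6.2.3, replace BD_NANO_ORDER with a variable that records, for each row, whether that injection was the first or second of its pair. Adding the PN × BD_NANO_ORDER interaction to the existing terms captures the same effect. Use the same position variable for the within-pair order term in the time models of SAP 6.2.4.1, where code has yet to be written. Keep BD_NANO_ORDER in the pair-level pain and force models, and define both variables in SAP 6.1. The cost is one derived variable and a line of code. The randomisation schedule already gives the order, so no new data are needed.

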6.2.4.1 Delivery time and Total injection time

A mixed effect model will be used (fixed effects of pen needle type, abdomen site, order of pair, order of pen needle within pair and random subject effect) to estimate average difference (BD PN - Terumo PN) in delivery time and total injection time. A Box-Cox transformation might be used to normalize the data if necessary. The upper bound of the confidence interval will be compared to 0: superiority will be concluded given that the upper bound of the 95% interval for the average difference is < 0 seconds.

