Analysis for time to deliver and dwell time: A mixed effect model will be used (fixed effects of pen needle type, abdomen site, order of pair, order of pen needle within pair and random Subject effect) to estimate average difference (BD PN – Terumo PN) in time to deliver and dwell time. The upper bound of the confidence interval will be compared to 0: superiority will be concluded given that the upper bound of the 95% interval for the average difference is  $< 0$  seconds.

Other exploratory endpoints will be summarized.

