2.5.3 Exploratory Objectives

No formal acceptance criterion has been established for the following objectives - time to deliver dose, total injection time, and survey responses after all injections completed.

3 Sample Size

Leakage data is currently being used to calculate sample size.

Based on previous study data (BDT-2P00116) where leakage is equal to or greater than 1.5U was observed in 20/298 (6.7%) of injections performed with Terumo Nanopass® and in 3/297 (1%) of injections performed with BD Nano™ PRO, a simulation was performed (code found in SVN repository under DBC-18PENDL01Size Bayesian prior proportion.R) indicating that 292 injections per each pen needle type would provide 90% power to show BD Nano™ PRO superiority to Terumo Nanopass®. If each Subject tests 6 pairs of pen needles, 292 injections per each pen needle requires 49 subjects (rounded to 50 subjects). 50 Subjects will generate data for 600 pen needles: 300 pen needle pairs - 300 BD Nano™ PRO and 300 Terumo Nanopass®. A 10% buffer was added (to compensate for subject attrition or unusable data), leading to a planned enrollment number of 55 subjects.

Pain: Assuming the SD for relative VAS is around 50mm (based on DBC-17NUCLS07), a sample size of 300 pairs (50 Subjects x 6 pairs) has >90% power of passing a -10mm NI criteria, assuming a true average of -0.5mm in favor of Terumo Nanopass® (based on a 2-sided 95% CI for the mean).

4 Intended Statistical Software

This document was generated with R version 3.5.1 (2018-07-02) and the following packages (version) were used: assertthat (0.2.0), base (3.5.1), BD basics (0.2.4), bindr (0.1.1), bindrcpp (0.2.2), colorspace (1.3.2), compiler (3.5.1), crayon (1.3.4), datasets (3.5.1), dplyr (0.7.6), ggplot2 (3.0.0), glue (1.3.0), graphics (3.5.1), grDevices (3.5.1), grid (3.5.1), gtable (0.2.0), lattice (0.20.35), lazyeval (0.2.1), magrittr (1.5), methods (3.5.1), munsell (0.5.0), nlme (3.1.137), pillar (1.3.0), pkgconfig (2.0.2), plyr (1.8.4), purrr (0.2.5), R6 (2.2.2), Rcpp (0.12.18), reshape2 (1.4.3), rJava (0.9.10), rlang (0.2.2), scales (1.0.0), stats (3.5.1), stringi (1.1.7), stringr (1.3.1), tibble (1.4.2), tidyselect (0.2.4), tools (3.5.1), utils (3.5.1), withr (2.1.2), xlsx (0.6.1), xlsxjars (0.6.1), xtable (1.8.3).

The study will be conducted within the same environment or more recent versions.

5 Data

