8.1.3 Executive Summary

A high level summary will be provided for each objective/endpoint (example below).

Primary Objective (examples only):

- *Injection Pain:* The lower bound of the CI for the average relative pain comparison between BD Nano™ PRO and Terumo Nanopass® met both non-inferiority and superiority criteria.

Secondary Objectives (examples only):

- *Injection force:* The lower bound of the CI for the average difference in rating of BD Nano™ PRO and Terumo Nanopass® injection force met the superiority criterion.
- *Needle Bending:* The upper bound of the CI for the average difference in percentage of needle bending occurrence with BD Nano™ PRO and Terumo Nanopass® met the superiority criterion.
- *Leakage:* The upper bound of the CI for the average difference in percentage of leakage occurrence with BD Nano™ PRO and Terumo Nanopass® met the superiority criterion.

In addition, a summary table for all primary and secondary objectives will be presented as in Table 2 (Example only). A blue check mark (✓) indicates that the acceptance criterion is met, while a red X mark (✗) indicates that the acceptance criterion is not met.

Table 2: Results Summary of primary and secondary objectives (Example only)

Objective	
Primary Objective	
Injection Pain (Non-inferiority)	✗
Injection Pain (Superiority)	✗
Secondary Objective	
Injection force	✓
Needle Bending	✓
Leakage	✓

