8.2.5 Exploratory Objectives

Patient end needle breaking will be summarized as in Section [8.2.3](#).

Summary statistics for delivery time and total injection time will be presented as in Table [12](#). The average difference (BD PN - Terumo PN) in delivery time and total injection time will be evaluated as presented in Table [13](#).

Table 12: Summary Statistics for delivery time (Example only)

Pen Needle	N	SD	Mean	Median	Range
BD Nano	31	40.52	142.03	142.00	90,274
Terumo Nanopass	31	63.90	165.84	140.00	91,362

Table 13: Mean difference of Delivery time and Total injection time with confidence interval (reciprocal of number of seconds). The last column indicates whether superiority was met or not. (Example only)

	Mean difference	95% Lower bound	P value	Lower bound >0 (Superiority)
Delivery time	0.000739	-0.000180	0.113	Fail
Total injection time	0.000452	-0.000180	0.279	Fail

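### Does the optional, loosely specified Box-Cox transform of injection times leave the superiority verdict open?

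*SAP*

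**What the plan says.** Protocol 13.3 models time to deliver and dwell time with fixed effects for needle, abdomen site, pair order and order within pair, plus a random subject effect. The BD needle is superior if the upper 95% bound of the BD minus Terumo difference is below 0 seconds. No transform is mentioned.

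SAP 6.2.4.1 applies the same model to delivery time and total injection time. It adds "A Box-Cox transformation might be used to normalize the data if necessary", then keeps the rule in seconds: "superiority will be concluded given that the upper bound of the 95% interval for the average difference is < 0 seconds".

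The only transformed scale shown is in example Table 13 (SAP 8.2.5), captioned "Mean difference of Delivery time and Total injection time with confidence interval (reciprocal of number of seconds"). Its verdict column requires a lower bound above 0. Section 6.2.4.1 does not refer to this table.

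On the status of these endpoints, SAP 2.5.3 says: "No formal acceptance criterion has been established for the following objectives - time to deliver dose, total injection time". Protocol 3.3 says the same of time to deliver and dwell time. SAP 8.1.3 says that "a summary table for all primary and secondary objectives will be presented as in Table 2", so the times do not appear there.

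**The concern.** The transform is optional, its trigger is unstated, and nothing says how the power is picked or whether the scaled Box-Cox form or a plain power is meant. The written rule stays in seconds even if the analysis does not. Read literally on reciprocal seconds, an upper bound below 0 would credit the slower needle.

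Two analysts who both follow the SAP could therefore work on different scales, and the scales need not agree. At stake is a reported superiority verdict on two endpoints that bear on the study rationale: Protocol 1.0 suggests that the thinner needle may need more force or more time. If the scale were chosen after seeing the needle contrast, the chance of a false verdict would also rise.

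**Working it through.** No sample size, power or error rate in the documents depends on the time scale, so there is no stated figure to reproduce. Two checks apply.

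**1. Does the direction of the rule hold on each scale?**

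| Scale | Faster BD needle means | Matching rule | Where written |
|---|---|---|---|
| Seconds | BD minus Terumo negative | upper bound < 0 | Protocol 13.3, SAP 6.2.4.1 |
| Log, or scaled Box-Cox (order-preserving) | negative | upper bound < 0 | same rule carries over |
| Plain reciprocal | positive | lower bound > 0 | SAP Table 13 |

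All three credit the faster needle. The table layout already gives the reciprocal its correct bound; only the cross-reference is missing.

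**2. How often do verdicts differ when each scale uses its correct rule?**

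Inputs from the documents: 50 subjects x 6 pairs = 300 injections per needle (Protocol 13.1) and a two-sided 5% level (SAP 6.2).

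Assumed inputs, because the documents give no real timing data: lognormal times, between-subject CV 30%, within-subject CV 30% or 50%, and the BD needle faster by 0, 5 or 10%. No order or site effects were simulated or fitted.

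In this balanced layout the needle contrast d is the difference of the two needle means on the chosen scale, with

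- SE = sqrt(2 x residual mean square / 300)
- df = 600 - 50 - 1 = 549
- BD superior if d + t(0.975, 549) x SE < 0, with the sign reversed for the plain reciprocal.

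Share of simulated trials (10,000 per setting) declaring BD superior:

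| Within-subject CV | BD faster by | Seconds | Log | Reciprocal | Seconds and log disagree |
|---|---|---|---|---|---|
| 30% | 5% | 52.0% | 56.9% | 51.5% | about 12 to 13% |
| 50% | 10% | 69.5% | 77.8% | 69.5% | about 13% |
| 30% | 10% | 98.5% | 99.4% | 98.6% | about 1% |

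With equal times, each scale alone declares BD superior in 2.4 to 2.6% of trials, against a nominal 2.5% in that direction. Taking whichever of seconds or log is more favourable gives about 3.3%.

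**Which pair of scales matters?** Seconds and reciprocal disagree more often (21.6% and 23.2% in the first two rows), and the best of all three scales gives a null rate a little above 4%. But Box-Cox is not a free menu. When the power was estimated by likelihood on data simulated this way (400 trials per setting), it averaged about 0 and stayed between -0.30 and 0.25. That points to the log; a power of -1 was never selected. Seconds against log is therefore the relevant comparison for data of this shape.

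**The case for a change.** The strongest case for a change is that a verdict which will be printed should have a defined scale, and that one or two sentences would supply it. That the text is loose is true: 6.2.4.1 has no trigger, no rule for the power and no pointer to Table 13. The verdict can also depend on scale.

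The case can be made to look larger through unequal spread. Taking the Table 12 CVs (40.52/142.03 = 28.5% for BD, 63.90/165.84 = 38.5% for Terumo) as within-subject values, with the BD median 5% lower, the superiority rates become 79.9% on seconds, 47.3% on log and 11.5% on reciprocal. The principle stands: when spreads differ, the scales compare different quantities. The figures carry little weight, for three reasons.

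- The SAP says in section 8 that its example values are not representative.
- Table 12 does not label its SDs as within-subject. Adding a 30% between-subject CV lifts the total CVs to sqrt(1.09 x 1.0812 - 1) = 42% and sqrt(1.09 x 1.1482 - 1) = 50%, above the values they came from.
- The 11.5% needs the reciprocal, which likelihood selection did not pick in the lognormal settings.

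Nor can Tables 12 and 13 be set against each other as a worked conflict. The SAP does not say that they share a sample, and the bound in Table 12 units depends on an unknown within-pair correlation.

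A conflict with the protocol is also hard to sustain. Protocol 13.0 delegates statistical detail to the SAP, and Protocol 13.3 models dwell time rather than total injection time, so its difference in seconds covers only one of Table 13's two rows.

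**Conclusion.** The wording is incomplete, but the gap is one that analysts fill sensibly. The method and its purpose are named, the direction of the rule is clear on every scale, and Table 13 shows the bound that goes with the reciprocal. Each scale alone holds its error at about 2.5% in the direction of a BD claim. Summary statistics by needle are also planned on the recorded scale (Table 12), so a transformed analysis would not hide the raw comparison.

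The size is small: about 12 to 14% disagreement between seconds and log in borderline settings, about 1% when the effect is clear, and a null rate of about 3.3% if the better of the two were always chosen. These figures rest on assumed lognormal times with equal spread for both needles and the stated CVs. They show that the scale can matter, not how often it will in this trial. Both endpoints are exploratory, neither enters the acceptance summary, and no primary or secondary conclusion is affected. No change to the plan is needed.
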